10.0 STUDY AGENTS

10.1 Preparation and Labeling

The Investigational Drug Service (IDS) pharmacist will ensure that all study drugs are stored in a secured area, under recommended storage conditions (below 86° F and protected from moisture and freezing) in accordance with applicable regulatory requirements and will be dispensed by qualified staff members. The pharmacist will maintain accurate records regarding study drug administration and return.

10.2 Omega-3 fish oil formulation

Prescription grade omega-3 fish oil supplementation will be used in the form of oral Lovaza (omega-3-acid ethyl esters) manufactured by GlaxoSmithKline. Subjects will be randomized to a dosage of either 1 or 4 capsules daily. We will use matching placebo capsules provided by the manufacturer so that all participants are taking 2 capsules twice daily – with food as recommended in clinical practice.

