Title of Study Protocol: **Fish oils and Adipose Inflammation Reduction (FAIR Study)**

Principal Investigator: **[name], MsTR**

Sponsors of Protocol: **National Institutes of Health**

Grants: **1K23DK095913-01A1 (NIDDK): Omega-3 PUFA suppress adipochemokines (PI:[name])**

IRB Protocol Number: **818359**

Date of Document: **November 4, 2014**

Synopsis

Title	Fish oils and Adipose Inflammation Reduction (FAIR Study)
Short Title	FAIR Study
Protocol Number	818359
Study Design	Parallel arm, double blind, placebo-controlled trial
Study Center(s)	University of Pennsylvania Medical Center Philadelphia, PA USA
Objective	To examine the effect of omega-3 fish oil supplementation
Study Population, Diagnosis And Main Inclusion Criteria	Obese (BMI>30), non-diabetic men and non-pregnant/non-lactating women aged 18-50 not currently consuming significant amounts of omega 3 fatty acids.
Study Product, Dose, Route, Regimen, Duration of administration	Participants will be randomized to placebo of Lovaza 4 grams/day orally. Subjects will be treated for 8 weeks.
Reference therapy	Placebo
Pharmacodynamic Evaluations	Inflammatory markers (cytokines, chemokines, acute phase proteins), metabolic markers, oral microbiome composition, monocyte function and lipoproteins
Safety Evaluations	Clinical and laboratory measurements will be taken at screening and upon completion of the study.
Statistical Methodology	Analysis will compare within group and between group differences to determine effect of omega 3 fatty acids vs placebo on all measures indicated

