4.0 STUDY DESIGN AND RATIONALE

We propose to conduct a parallel arm, double blind, placebo-controlled trial to understand the anti-inflammatory and metabolic effects of marine derived omega-3 fatty acids (EPA + DHA) on obesity-related inflammation and chemokine signaling in humans. Obese (BMI > 30 kg/m²) but non-diabetic young males and females (n ~ 44; 25 to 50 years of age) taking no omega-3 fatty acid (EPA + DHA) supplements and consuming a low fish diet (defined as usual intake of high omega-3 fish (tuna and other non-fried fish) < 3 to 4 servings per month) will be included. A low habitual fish intake is important to control EPA + DHA intake during the supplement period (see exclusion criteria below). Subjects also will be required to maintain their current fish intake throughout the treatment period.

There will be two treatment groups; (1) placebo and (2) omega-3 fatty acids 4 grams/day. The trial will be randomized, double blind, placebo-controlled, with parallel treatment groups; treatment with omega-3 fatty acids 8 weeks. We will enroll participants until at least 22 subjects per study-arm complete all study visits (i.e., at least 44

participants).

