4.1 Drug, Dose Selection and Duration

Prescription Lovaza (omega-3-acid ethyl esters) from GlaxoSmithKline at 4 grams day (2 1-gram capsules twice daily, with food) will be used. We expect this dose to be safe because it is a dose that is recommended, and routinely used, for management of moderate or worse hypertriglyceridemia (levels ≥ 400 mg/dL). We will use matching placebo capsules so that all participants are taking 2 capsules twice daily – with food as recommended in clinical practice.

The study duration was chosen in order to provide adequate time for potential anti-inflammatory effects of treatments without requiring maximum lipid modifying effects while also reducing the potential for drop-out and loss to follow up that is associated with longer study durations.

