In order to establish effects of treatments on adipose inflammatory parameters, we will obtain gluteal region subcutaneous adipose tissue biopsies under local anesthesia (2% Lidocaine). A detailed description of the adipose collection procedures is given in Section 6.4. Participants will then be randomized to drug or placebo group. Supplies of study drug will be provided to last 8 weeks (4 pills/day of either Lovaza or placebo).

Participants will be provided verbal and written instruction to take the study drugs as follows; 2 fish oil/placebo with food in the morning, 2 fish oil/placebo with food in the evening. A pill diary will be given to all subjects.

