10.3 Study Agent Compliance

Study drug adherence will be monitored by pill count and medication diary and will be assessed by telephone/email contact at 4 weeks after randomization and in person at Visit 4 (8 weeks after randomization). The final analysis of compliance will be performed at this time.

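### Section 10.2 allocates subjects to 1 or 4 capsules daily, which contradicts the placebo versus Lovaza 4 g/day design set out elsewhere

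*Combined protocol and SAP*

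**What the plan says.** Section 10.2, which describes the study drug, says: "Subjects will be randomized to a dosage of either 1 or 4 capsules daily". The sentence after it has every participant taking two capsules twice a day, with matching placebo supplied by the manufacturer.

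The allocation is described differently elsewhere:

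- **Synopsis:** "Participants will be randomized to placebo of Lovaza 4 grams/day orally" (the word between placebo and Lovaza is evidently meant to be 'or'). The reference therapy is listed as placebo.
- **Section 4.0:** "There will be two treatment groups; (1) placebo and (2) omega-3 fatty acids 4 grams/day".
- **Section 6.5.2, Visit 2:** "Participants will then be randomized to drug or placebo group", with an 8-week supply of four pills a day of one or the other.
- **Section 4.1:** Lovaza "at 4 grams day (2 1-gram capsules twice daily, with food) will be used", with matching placebo. This section gives the dose and the capsule burden but does not list the arms.
- **Sections 3.0 and 9.1:** the objectives and the sample size both compare omega-3 with placebo, without restating a dose.

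**The concern.** Section 10.2 is current operative text, and it follows directly after the pharmacist's storage, dispensing and record-keeping duties in Section 10.1. It is therefore a natural place for pharmacy staff to look for the dosing rule, and the rule it gives is not the trial's.

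The sentence does not say what a 1-capsule group would take. If a dispensing instruction or randomisation list were built from it, the control group might receive some active drug, and the trial would no longer have the placebo comparison that its objectives and power calculation assume.

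**Working it through.** **1. Can the sentence be read consistently with the rest of the protocol?** There are two readings.

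| Reading of '1 or 4 capsules' | Next sentence of 10.2 (all take 2 twice daily) | Synopsis, 4.0, 6.5.2 (a placebo arm) |
|---|---|---|
| Total capsules per day | Contradicted: one group would take 1, not 4 | Contradicted: no placebo arm named |
| Active capsules, topped up to 4 with placebo | Consistent | Contradicted: 1 g versus 4 g, no pure placebo arm |

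Neither reading works.

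**2. Which text is wrong?** The Synopsis, Section 4.0 and Section 6.5.2 agree on the two arms, and Section 9.1 powers Lovaza against placebo. The dose arithmetic also points to a single active dose:

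- Per 1-gram capsule (Appendix D, Section 3.2): about 465 mg EPA and 375 mg DHA; 465 + 375 = 840 mg.
- Four capsules: 4 × 465 = 1,860 mg EPA; 4 × 375 = 1,500 mg DHA; total 3,360 mg/day.
- Section 2.0 gives 1,860 mg EPA and 1,500 mg DHA, so the figures match.

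**3. Does the sample size depend on the sentence?** Section 9.1 states 22 per group for a 0.9 SD difference between Lovaza and placebo, by a two-sample Wilcoxon test with 80% power and α = 0.05. Sides are not stated; two-sided is assumed.

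- Normal approximation: n = 2 × ((1.960 + 0.842)/0.9)² = 19.4, so 20 per group.
- Divided by the Wilcoxon efficiency under normality (3/π = 0.955): 20.3, so 21.
- Divided by the worst-case efficiency of 0.864: 22.4.
- Simulated Wilcoxon power at 22 per group and 0.9 SD, normal data: about 81%.

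The stated 22 reproduces to within a patient or two. It is a Lovaza versus placebo calculation, and correcting Section 10.2 leaves it unchanged.

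**4. What would following Section 10.2 do?** This is a bounding exercise on the top-up reading, which no section describes. It assumes that the placebo contains no EPA or DHA; the protocol does not give its composition.

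| | As planned | Top-up reading |
|---|---|---|
| Active arm, EPA+DHA | 3,360 mg/day | 3,360 mg/day |
| Control arm, EPA+DHA from study capsules | 0 mg/day | 840 mg/day (840/3,360 = 25%) |
| Dose difference between arms | 3,360 mg/day | 3,360 − 840 = 2,520 mg/day (75% of planned) |
| Control capsules over a nominal 56 days | 0 Lovaza + 224 placebo = 224 | 56 Lovaza + 168 placebo = 224 |

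**5. Would it be noticed?** Section 10.3 says "Study drug adherence will be monitored by pill count and medication diary". Both count 4 capsules a day in either case, so neither would reveal the difference. Two other sources could. One is the pharmacy file, since Section 10.1 says "The pharmacist will maintain accurate records regarding study drug administration and return". The other is the serum and urine EPA and DHA levels listed as exploratory in Section 3.0.

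**The case against.** The strongest reply is that this is a drafting slip that misleads nobody. The Visit 2 text, which governs randomisation and supply, is explicit about drug or placebo at four pills a day. Section 10.2 itself fixes the capsule burden at four a day with matching placebo in its next sentence. No planned figure depends on the wrong wording. The 840 mg/day figure measures a scenario that the protocol never describes, and nothing in the documents shows that the pharmacy used Section 10.2.

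Most of that stands. The intended design is not in doubt, and the dose calculation only bounds what could follow; it is not an effect of the plan as written. Section 4.1 should be cited for the dose and the matching placebo, not for the arms. The 224 capsules are a nominal 8-week count, and Appendix A allows completion between Weeks 7 and 9.

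What does not stand is the inference that the sentence can be left alone. It gives a wrong allocation rule in the study-drug section, no reading of it fits the trial, and no other text corrects it.

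**Conclusion.** The concern holds, as a minor inconsistency. The allocation sentence in Section 10.2 is wrong; the Synopsis and Sections 4.0 and 6.5.2 carry the intended design.

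The effect on the statistical plan is nil: the comparison, endpoint, Wilcoxon test and 22 completers per arm are unchanged. The exposure is operational. Controls would receive 0 mg/day of EPA+DHA from study capsules if Section 6.5.2 is followed, and about 840 mg/day if the top-up reading of Section 10.2 were followed. That range assumes a placebo free of EPA and DHA and the labelled capsule content. The conclusion that the sentence is wrong rests on neither assumption; it follows from the text alone.

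**What to change.** Replace the sentence in Section 10.2 with:

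> Subjects will be randomized to 4 capsules daily (2 capsules twice daily) of either Lovaza or matching placebo.

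Then confirm that the randomisation list and the pharmacy dispensing instructions, neither of which is in the documents, match Section 6.5.2.

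The cost is a one-sentence protocol correction and a short document check. Arms, endpoint, sample size, test and participant procedures stay as they are.

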10.3 Study Agent Compliance

Study drug adherence will be monitored by pill count and medication diary and will be assessed by telephone/email contact at 4 weeks after randomization and in person at Visit 4 (8 weeks after randomization). The final analysis of compliance will be performed at this time.

11.0 POTENTIAL RISKS

A complete description of all study related risks is also provided in the Safety Plan (Appendix D). Briefly, risks include (1) general study procedure-related risks (e.g., blood draws, intravenous lines, adipose biopsies), (2) Lovaza related risks [e.g., increase in alanine aminotransferase (ALT) and/or low-density lipoprotein cholesterol (LDL-C) levels], and (3) risks from clinical or laboratory abnormalities that emerge during the study. The process of monitoring the study is outlined in the Safety Plan for proposed Data Safety and Monitoring Board (DSMB) (Appendix D). Additional safety-related details are provided in the Safety Plan

12.0 POTENTIAL BENEFIT OF THE PROPOSED RESEARCH

There is no direct benefit to the participant of this study; however data obtained from this study may be very useful in understanding the role of omega-3 fatty acids on obesity-related inflammatory and metabolic complications. Subjects on study drug may have

temporary improvement in triglyceride levels while in the study. Clinical data relating to general health and risk for metabolic disease (diabetes, cholesterol) will be provided to them and their primary physician if they so wish.

13.0 ADVERSE EVENTS

A complete description of all study related risks, adverse events, adverse event definitions, recording and reporting is provided in the Safety Plan (Appendix D for proposed Data Safety and Monitoring Board (DSMB)). Key aspects are summarized below.

13.1 Non-serious Adverse Events

All other observed or volunteered adverse events regardless of treatment group or suspected causal relationship to study drug will be recorded on the adverse event source document and transcribed onto the case report form. Events involving adverse drug reactions, illnesses with onset during the study, or exacerbations of pre-existing illnesses will be recorded. In addition, abnormal objective test findings (e.g., electrocardiogram changes, abnormal laboratory test results) that result in a change in study drug dosage or in discontinuation of the drug, or require intervention or diagnostic evaluation to assess the risk to the patient/participant, will be recorded as adverse events. Clinically significant changes in physical examination findings will also be recorded as adverse events.

Thus, any AE that is not designated as Serious, but is not expected as defined in appendix D, must be recorded on the non-serious AE page of the CRF.

13.2 Serious Adverse Event

All serious adverse events (as defined below) regardless of treatment group or suspected relationship to study drug will be reported to the DSMB, NIH, FDA and University of Pennsylvania IRB as outlined by the Penn Manual for Clinical Research (Office of Human Research).

A serious adverse event (SAE) is any AE that:

- ◆ Results in death
- ◆ Is life-threatening (at immediate risk of death from the event as it occurred)
- ◆ Requires inpatient hospitalization (overnight stay) or prolongs a current hospitalization
- ◆ Causes a persistent or significant disability/incapacity
- ◆ Is a congenital anomaly/birth defect in the offspring of a patient who received test article

And may be any event that:

- ◆ Requires intervention to prevent one of the outcomes listed above

The investigator should exercise medical and scientific judgment when deciding whether expedited reporting is appropriate in other situations not strictly meeting the listed criteria above.

13.3 Intensity

The investigator is responsible for ensuring that AEs are documented on the appropriate page of the CRF according to the following descriptors:

Mild: associated with no limitation of usual activities or only slight discomfort

Moderate: associated with limitation of usual activities or significant discomfort

Severe: associated with inability to carry out usual activities or very marked discomfort

13.4 Relationship to Test Article

The relationship of AEs to study drug will be assigned by the investigator according to the following definitions:

Definitely: a reaction that follows a reasonable temporal sequence from administration of the test article; that follows a known or expected response pattern to the suspected study drug; and that cannot be reasonably explained by the known characteristics of that subject/patient's clinical state.

Probable: a reaction that follows a reasonable temporal sequence from administration of the test article; that follows a known or expected response pattern to the suspected study drug; and that is unlikely explained by the known characteristics of that subject/patient's clinical state.

Possible: a reaction that follows a reasonable temporal sequence from administration of the test article; that follows a known or expected response pattern to the suspected study drug; but that could readily have been produced by a number of other factors.

Unlikely: a reaction that does not follow a reasonable temporal sequence from administration of the test article. However, causality from the test article cannot be ruled out.

None: a reaction for which sufficient data exist to indicate that the etiology is unrelated to the study drug.

13.5 Pretreatment-Emergent Events

Events that occur between the time the informed consent document is signed for the study and the time when the patient is first exposed to study drug as “pretreatment-emergent” events. These pretreatment-emergent events will not be collected as adverse events, unless the event increases in intensity or frequency after study article administration.

13.6 Recording and Documenting AEs and SAEs

The investigator or study team member must completely and promptly record each AE in the database on the AE record, even if the relationship of an AE to the study drug is assessed by the investigator to be “unlikely” or “none”. The investigator should attempt, if possible, to establish a diagnosis based on the presenting signs and symptoms.

14.0 INVESTIGATOR OBLIGATIONS

This section reviews each investigator’s obligations according to federal regulations.

14.1 Adverse Event Reporting Obligations

The investigator is responsible for recording AE’s reported by the subject or discovered by any other means during the study. In addition, AE’s classified as “serious” must be reported to the DSMB, NIH, and University of Pennsylvania IRB as outlined by the Penn Manual for Clinical Research (Office of Human Research).

14.2 Study Records and Source Documents

Federal regulations and The University of Pennsylvania policy require that, following completion of a clinical study, a copy of all records of that study be maintained by the Principal Investigator. Completed original CRFs and clarification queries, dated, and signed by the investigator, will be kept at the study site beyond locked door and key. Hard copies of data forms will also be kept on file at The University of Pennsylvania or its designee.

In order to assure the accuracy of data collected in the CRFs, it is mandatory that The University of Pennsylvania or its designees, as well as representatives of the FDA or other pertinent regulatory agencies, have access to original source documents (e.g., patient records, patient charts, laboratory reports). During the review of these documents, the anonymity of the patient will be respected with strict adherence to professional standards of confidentiality.

The University of Pennsylvania reserves the right to terminate the study for refusal of the investigator to supply source documentation of work performed in this clinical study.

APPENDIX A

Study Visits and Procedures

Procedure	Visit 1	Visit 2	Visit 3	Visit 4
	Screen	Randomization	Contact Follow-up	Completion
	Week -2 to -4	Week 0	Week 4	Week 7-9
Participant Questionnaire completion ¹	X			
Informed consent	X			
History & physical	X			
3 day diet record, Food History questionnaire		X	X	
Electrocardiogram	X			X
Blood pressure, heart rate, weight, height & waist measures	X	X		X
Glucose and insulin measurement	X			X
Urine pregnancy test ²	X	X		X
Review medications	X	X	X	X
Dispense study medication/placebo pills		X		
Comprehensive Metabolic Lab Panel ³	X			X
Complete blood count (CBC)	X			X
Lipid profile ⁴	X			X
Blood and urine collected for efficacy measures		X		X
Dietary assessment of high omega-3 fish consumption (questionnaire)	X	X	X	X
Saliva Collection		X		X
Adipose biopsy		X		X

- ¹ The questionnaire along with a copy of the consent form will be mailed to subjects for completion prior to the study visit in order to save time on the day of their screening visit. After consent is obtained, a coordinator will review the questionnaire with the participant for completeness.
- ² Standard urine pregnancy test performed on females of child-bearing potential only
- ³ Comprehensive Metabolic panel includes: sodium, potassium, chloride, carbon dioxide, glucose, blood urea nitrogen, creatinine, calcium, total protein, albumin, AST, ALT, alkaline phosphatase, and total bilirubin
- ⁴ Includes TC, LDL-C, VLDL, HDL-C, TG

APPENDIX B

Pre-screening E-mail Questionnaire

Hello,

Thank you for your interest in the FAIR study. We are looking for healthy volunteers to participate in a study to better understand the anti-inflammatory benefits of prescription fish oil supplements that are currently used to help people with cholesterol problems. If you qualify, your participation would last about 3 months during which time there are 3 visits to the Clinical and Translational Research Center (CTRC) at the Hospital of the University of Pennsylvania.

Visit 1 is an outpatient screening visit which is about 2 hours long.

Visit 2 is a baseline visit which lasts about 2 hours

Visit 3 is a follow-up visit conducted via e-mail and/or telephone (you do not need to come to the CTRC)

Visit 4 is a completion visit which lasts about 2 hours

Visits may include blood sampling, urine collection, blood pressure measurements, fat-tissue sampling, fasting and brief physical exams.

Volunteers who complete all study visits will be compensated \$180 for time and travel.

If you would like more information and to see if you may qualify, please answer the questions below and reply back to me. A member of our study team will be in touch with you as soon as possible.

- 1) Name:
- 2) Gender:
- 3) Phone Number:
- 4) Email:
- 5) Age:
- 6) How did you hear about the study?
- 7) Do you have a history of diabetes (type 1 or type 2) or are you on any medications to lower your blood sugar?

- 8) Do you have any history of abnormal heart rhythm or other heart problems?
 1. If yes, what are they?
- 9) Do you have any other medical conditions for which you are under a doctor's care?
 1. If yes, what are they?
- 10) What is your height?
- 11) What is your weight?
- 12) How often do you eat-- as a main course-- tuna or other non-fried fish? (One serving size is 3 oz = in size to a deck of cards. Note: One serving of non-fried fish could include: 1, 3 oz. filet of salmon OR 6 pieces of sushi OR 8 sushi rolls OR ~4 tuna fish (salad) sandwiches, etc.)
 - A) Once or less per month
 - B) 2-3 times per month
 - C) Once per week
 - D) Twice per week
 - E) More than twice per week
- 13) Have you taken any fish oil supplements in the past 3 months?
- 14) What medicines, including supplements (like Omega-3 or fish oil) and vitamins, do you currently take and how often do you take them?
 - 1.
 - 2.
 - 3.
 - 4.
 - 5.
- 15) Do you have any history of gall bladder disease?
- 16) Do you have any allergies to fish?
- 17) Do you currently smoke or use any other tobacco product (snuff, chew, dip, etc.)?
 1. If no, have you used tobacco in the last 30 days?
- 18) On average, how many days per week do you drink alcohol?
- 19) On a day when you drink alcohol, how many alcoholic drinks do you have?
- 20) When you drink alcohol, is it beer, wine or liquor?
- 21) How many ounces are in each drink?
- 22) Do you have high blood pressure?
- 23) Do you have a history in your immediate family of pre-mature heart disease or stroke (i.e., mother/sister before age 65 or father/brother before age 55)?
 1. If yes, who and at what age?
- 24) Have you been treated for cancer?
 1. If yes, are you still being treated?
 - i. If you are not still being treated, when was your last treatment?
- 25) Are you HIV + or do you have AIDS?
- 26) *Females only:* Are you currently pregnant or breast-feeding?

- 27) Are you currently enrolled in another research study?
1. If yes, when will your participation end?
- 28) Have you participated in a clinical research study within the last 6 weeks?
- 29) In terms of race, do you consider yourself a Caucasian, African American, Asian, Pacific Islander, Hawaiian Native, American Indian or Alaskan Native?

I look forward to your reply and thank you for your time.

Sincerely,

